10.8.2 Pharmacokinetics

Blood samples for maltol and maltol glucuronide on each PK day

Blood samples will be collected at the required times on the PK assessment days relative to the time of ferric maltol morning dosing: pre-dose then two further times between 0.5-10 hours post-dose in the 2-17 years age group and pre-dose then three further times between 1-12 hours post-dose in the 1 m to less than 2 years age group (see Section 10.3 and section 10.4).

Following collection and mixing, blood samples will be centrifuged, and the resultant plasma samples separated and stored at -20°C at the study site, prior to collection and onward shipping to the central laboratory on dry ice for subsequent assay of maltol and maltol glucuronide plasma concentrations using appropriately validated bioanalytical methods. Full

CONFIDENTIAL Page 61 of 80

details of the required sample collection, processing and handling logistics will be specified in the study specific Laboratory Manual. Samples will be destroyed at the end of the study, once all analyses are complete.

Blood samples for iron markers on each PK day

Blood samples will be collected at the required times on the PK assessment days, relative to the time of ferric maltol dosing: pre-dose then two further times between 0.5-6 hours post-dose in the 2-17 yrs age group. Same times as blood samples for maltol/maltol glucuronide for each individual (see Section 10.3 and section 10.4.).

Following collection and mixing, blood samples will be centrifuged, and the resultant serum samples separated and split into 2 aliquots at each timepoint. Ambient serum samples will be shipped to the central laboratory for subsequent assay of serum iron, transferrin, transferrin saturation (TSAT), total and unsaturated iron binding capacity (TIBC, UIBC. Frozen serum aliquot will be stored at site (-20°C) for later onward shipping on dry ice to the central laboratory. Full details of the required sample collection, processing and handling logistics will be specified in the study specific Laboratory Manual. Samples will be destroyed at the end of the study, once all analyses are complete.

PK blood sample scheduling in the 2-17 yrs age groups:

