12.2.4 Imputation of Missing Data

All data will be used according to availability, with no imputation for missing data.

CONFIDENTIAL Page 72 of 80

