 - Subjects randomised to ferrous sulfate oral liquid will not need to complete the PK period, they will remain on oral ferrous sulfate liquid until Week 12.
 - Ferrous sulfate 125 mg/ml (25 mg elemental iron) or equivalent dose will be used for all children/adolescents. To maximise the iron replenishment for subjects within this group as well; aged 2 17 yrs will be dosed 0.24ml (6mg elemental iron) per kg body weight per day, up to a maximum of 8ml given daily in two divided doses.
- Assigned treatment phase: 12 weeks open label treatment for ferric maltol children aged
 1 month to less than 2 years.

- Once the PK samples collected from the pre-assignment phase have been analysed for subjects aged 1 month to less than 2 years, and following data review it has been confirmed that they can enroll in the treatment phase, they will be assigned to receive ferric maltol oral suspension and start the 0.1 ml/kg/dose, BID (Maximum 2.5ml BID) dose on Visit 2 and continue for 7-10 days. On Visit 3 (PK Day 2), following baseline pre-dose blood sample and urine sample, subjects will take a single dose of 0.1 ml/kg ferric maltol suspension under supervision. Further three PK blood and urine samples will be collected up to 12 hours post dose. Subjects will continue until week 12.
- End of study: Week 12 visit.
- Post-treatment safety follow-up: 10-14 days following study completion of the treatment period or premature discontinuation.

Table 2.1: Schedule of Assessments for subjects aged 2 years-17 years.

	SCREENING		TREATMENT				FOLLOW- UP
Duration	Up to 21 days	(e	12 quivale	: WEE		ays)	10-14 days
Day		1	7- 10	28	56	84	94-98
Visit 11	1	2	3 8	4	5	6	7 ^{9,10}
Informed Consent	х						
Eligibility ^{1,8}	х	х	х				
Demographics	Х						
Medical History	х						
Physical Examination	х					х	
Vital Signs ²	х	х	х	х	х	х	
Urine Pregnancy Test 4	х	х	х	Х	х	х	
Clinical Laboratory tests ⁵	х					х	
Haematology ⁶	х			Х		х	
Iron markers ⁶	х			Х		х	
PK assessment PK Blood Sampling for maltol/maltol glucuronide and iron markers ⁷		Х	х				
Randomisation ⁸		х					
Dispense Study Drug		х	Х	Х	Х		
Return Study Drug for Accountability			х	х	х	х	

	SCREENING	TREATMENT			FOLLOW- UP			
Duration	Up to 21 days	12 WEEKS (equivalent of 84 days)						
Day		1	1 7- 28 56 84		94-98			
Visit 11	1	2	3	4	5	6	7 ^{9,10}	
Palatability questionnaire		х		х				
Adverse Events		х	х	х	х	х	х	
Concomitant Medications and Procedures	х	х	х	х	х	Х	х	
Compliance reminder		х	х	х	х	х		

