3.2.4 Pharmacokinetic (PK) Population (Full Analysis Set)

The PK Population is defined as all randomised/assigned subjects who have had at least one dose of study drug and who have at least one evaluable post-dose PK sample (applicable only for ferric maltol group). All PK data will be analyzed using the PK population.

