3.4.2 Secondary Endpoints Analysis

The secondary endpoints will be reported for each treatment group using descriptive statistics summarised by mean, median, and range (minimum and maximum), and 95% confidence interval for the mean where applicable, split by age group.

Any measurement obtained after a patient received a blood transfusion, or received an intravenous iron or erythropoiesis stimulating agent (ESA) will be excluded from the analysis.

The secondary endpoints are as follows: PK analysis of Serum Iron, Corrected serum iron, TSAT, Transferrin, TIBC, UIBC, Maltol and Maltol Glucuronide.

Descriptive summary statistics will be summarised for children and adolescents aged 1 month to 17 years in the ferric maltol group for the PK analysis of Serum Iron, Corrected serum iron, TSAT, Transferrin, TIBC, UIBC, Maltol and Maltol Glucuronide.

Changes in iron markers from baseline to Weeks 4 and 12

The secondary analysis of the change from baseline to Weeks 4 and 12 in iron markers (serum iron, serum corrected iron, transferrin, TSAT, TIBC, UIBC and ferritin) will be summarised using descriptive summary statistics. In this analysis, missing Week 12 and Week 4 values will be imputed using a LOCF (last observation carried forward) approach in which the last available post-baseline measurement will be used in the analysis.

Achieving Hb concentration within normal range at Week 12

The number and percentage of subjects achieving normal range, based on the central laboratory's normal reference range, at Week 12 will be summarised by treatment group.

Qualitative assessments from subject questionnaires that allow evaluation of the acceptability, palatability and ease of use

Qualitative assessments from subject questionnaires that evaluate acceptability, palatability and ease of use will be summarised separately for children aged 5 and under and those aged 6 and over.

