0.1 ml/kg ferric maltol under supervision. Three PK Post-dose blood samples will be collected at the following windows 1.0-2.0 hrs, 3.0-4.0 hrs and 10.0-12.0 hrs; postdose urine samples will be taken between 0.5 hr -3 hrs, 3 hrs -6 hrs and 7 hrs -12hrs post dose.

In the event of an administered dose not being consumed or partially consumed by the patient this will be noted as a missed dose and will not be repeated.

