3.6.2 Clinical Laboratory Tests

Clinical Chemistry and Haematology will be collected at the Screening Visit and Visit 6 (Day 84). In addition, Haematology will be collected at Visit 4 (Day 28) for those subjects in the 2-17 years of age group. Additionally, Hematology and iron markers will be collected at Visit 2 for the 1 month to < 2 years age group.

At Visit 7, Clinical Chemistry and Haematology will be collected if the subject has an ongoing AE that requires onsite assessment/management, or if the subject early discontinued.

Chemistry parameters include vitamin B12, folate, alanine aminotransferase (ALT), aspartate aminotransferase (AST), alkaline phosphatase (ALP), gamma-glutamyl transpeptidase (GGT), total bilirubin, creatinine, amylase, blood urea nitrogen (BUN), phosphorous, sodium, potassium, chloride, calcium, total cholesterol, uric acid, glucose, total protein, albumin.

Haematology parameters include red blood cell count, haemoglobin, haematocrit, mean cell volume (MCV), white blood cell count (total and differential (% and absolute)), absolute reticulocyte count and platelet count.

Descriptive statistics for each safety laboratory parameter will be presented for baseline values and for values and the change from baseline at each post-baseline visit.

Values outside the normal range will be categorised as below the lower limit of normal or above the upper limit of normal based on the central laboratory's normal reference range. Values

outside of the normal range will be summarised. Shifts from baseline to worst post-baseline category will be tabulated by laboratory parameter and shift category (low to low, normal to low, high to low, low to normal, normal to normal, high to normal, low to high, normal to high or high to high) for chemistry and haematology parameters.

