4.3 Final Analysis

After all comments on the pre-final analysis have been resolved and the study database is declared final, the final analysis will be generated. Final TFLs will be provided approximately 1 week after the study database is declared final. If there were no changes to the pre-final analysis or the study database, the pre-final TFLs may be considered final. In addition to TFLs, SDTM (study data tabulation model) data and ADaM data along with associated files will be provided. Associated files may include: annotated CRFs, SDTM specifications, SDTM programs, ADaM specifications, ADaM programs, TFL programs, and CDISC (Clinical Data Interchange Standards Consortium) Define packages for both SDTM and ADaM data.

5 CHANGES FROM PROTOCOL-SPECIFIED STATISTICAL ANALYSES.

The primary analysis for change in Hb is based on mITT, and additional sensitivity analyses will be based on the ITT and PP population.

The addition of changes in iron markers from baseline to Week 4 as a secondary endpoint deviates from the secondary endpoints listed in section 6.4 of the protocol.

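### SAP 3.4.2 fills missing Week 4 and Week 12 iron markers by LOCF, which the protocol rules out and SAP section 5 does not declare; no suitable scheduled value exists to carry to Week 4

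*SAP*

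**What the plan says.** Protocol 12.2.4 is unconditional: "All data will be used according to availability, with no imputation for missing data". SAP 3.1.6 keeps this as the general rule but leaves room for exceptions stated elsewhere in the SAP. SAP 3.4.2 then makes one. For serum iron, corrected serum iron, transferrin, TSAT, TIBC, UIBC and ferritin, "missing Week 12 and Week 4 values will be imputed using a LOCF (last observation carried forward) approach in which the last available post-baseline measurement" supplies the value.

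SAP section 5, which lists changes from the protocol's analyses, has two entries. One is the mITT basis for the primary haemoglobin analysis, with ITT and PP as sensitivity analyses. The other reads "The addition of changes in iron markers from baseline to Week 4 as a secondary endpoint deviates from the secondary endpoints" and goes on to cite protocol 6.4. LOCF is not mentioned.

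**The concern.** There are two problems.

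- **Undeclared departure.** A reader who relies on section 5 would take the iron-marker tables to be observed data, as the protocol promises. They would contain imputed values.
- **The rule does not match the sampling schedule.** Carrying a value to Week 4 needs an earlier post-baseline value, and the routine schedule provides none. The only scheduled candidates are PK-day samples, which are timed around a dose and taken in one arm only. The SAP does not say whether they qualify, so two programmers working from it could produce different Week 4 tables.

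If PK samples qualify, scheduled data would fill gaps at ages 2-17 in the ferric maltol arm only, in tables presented by treatment group. Any confidence interval for the mean would treat carried values as observed. The values themselves could mislead: protocol 5.4.2 (adult study ST10-01-102) reports the largest change in serum iron and TSAT 2 h after dosing, so a post-dose sample may show acute absorption rather than iron status at four weeks.

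**Working it through.** The plan gives no figure to reproduce here. The check compares the rule with the two schedules of assessments and then counts subjects.

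**Scheduled iron markers after baseline**

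| Group | Before Day 28 | Day 28 | Day 84 |
|---|---|---|---|
| Ferric maltol, 2-17 y, PK subjects | PK samples, Day 1 and Day 7-10 | yes | yes |
| Ferric maltol, 2-17 y, other subjects | none | yes | yes |
| Ferrous sulfate, 2-17 y | none | yes | yes |
| Infants, 1 month to < 2 y | PK samples, Day 7-10 | none | yes |

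Sources: protocol 10.3 and 10.4; SAP Tables 2.1 and 2.2. For the comparator arm, SAP 2.2.1 states "Subjects randomised to ferrous sulfate oral liquid will not need to complete the PK period". For infants, SAP 3.6.2 adds only a pre-treatment collection: "Additionally, Hematology and iron markers will be collected at Visit 2 for the 1 month to < 2 years age group".

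**What the PK-day samples contain**

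- Assays (protocol 10.8.2): "subsequent assay of serum iron, transferrin, transferrin saturation (TSAT), total and unsaturated iron binding capacity". Ferritin is not in this list, although SAP 3.4.2 includes it in the LOCF.
- Timing at ages 2-17: pre-dose, then two samples 0.5-6 h after the dose.
- Timing in infants (SAP 3.5.1): pre-dose, then "Three PK Post-dose blood samples will be collected at the following windows 1.0-2.0 hrs, 3.0-4.0 hrs and 10.0-12.0 hrs".

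Read literally, the last available post-baseline measurement from a PK day is the final post-dose sample: up to 6 h after a dose at ages 2-17, and 10-12 h in infants.

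**Head count, from planned numbers**

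- PK subjects aged 2-17: 12 per age group × 2 = 24, all on ferric maltol.
- Ferric maltol with no scheduled iron value between baseline and Day 28: 49 − 24 = 25 of 49 (51%).
- Ferrous sulfate with none: 49 of 49.
- Both arms: 74 of 98 (75.5%).
- Ferritin: no subject has a scheduled value to carry to Week 4.

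**Size at ages 2-17 if PK samples count**

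Let p be the proportion of Week 4 values missing. The documents give no figure, so 5%, 10% and 20% are assumptions, applied equally to PK and other subjects.

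Carried values = 24p. Share of the ferric maltol Week 4 values = 24p / [49(1 − p) + 24p].

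| p | Carried | Share of ferric maltol values | Ferrous sulfate |
|---|---|---|---|
| 5% | 1.2 | 1.2 / 47.75 = 2.5% | 0 |
| 10% | 2.4 | 2.4 / 46.5 = 5.2% | 0 |
| 20% | 4.8 | 4.8 / 44.0 = 10.9% | 0 |

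The tables are split by age group. If an age group had only 12 ferric maltol subjects, all would be PK subjects and the share would be 12p / 12 = p, that is 5%, 10% or 20%.

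**Age of the carried value**

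- PK Day 2 to Week 4: 28 − 10 = 18 to 28 − 7 = 21 days. For infants this could supply up to 12 Week 4 results, ferritin excepted, with no Week 4 sample taken.
- PK Day 2 to Week 12 for an infant who drops out: 84 − 10 = 74 to 84 − 7 = 77 days.
- Week 4 to Week 12 at ages 2-17, either arm: 84 − 28 = 56 days.

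**If PK samples do not count:** there are 0 scheduled values to carry to Week 4, so that half of the rule does nothing for scheduled data.

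**The case against.** The conflict with protocol 12.2.4 and the silence of section 5 are not in dispute. The case against concerns the rest.

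- **The documents lean against using PK samples.** The schedules at ages 2-17 list routine iron markers and PK sampling in separate rows. PK data have their own section and population (SAP 3.2.4: "All PK data will be analyzed using the PK population"), while secondary efficacy uses ITT. Ferritin is in the LOCF list but not in the PK assay list. These are fair pointers, but protocol 10.8.2 calls the PK-day assays iron markers and no sentence excludes them. The ambiguity stands, and the percentages hold only on one reading of it.
- **Infants have nothing missing at Week 4, because nothing is scheduled.** That is a reasonable reading. However, 3.4.2 splits by age group and does not limit the Week 4 endpoint to ages 2-17, so the text does not settle it.
- **Unscheduled and early-termination samples could be carried in either arm** (SAP 3.1.2). This is correct, so the one-arm pattern applies to scheduled data only. For Visit 7 after early discontinuation, SAP 3.6.2 names chemistry and haematology but not iron markers, so it is uncertain whether such values would exist.
- **The missingness range is assumed, and no bias in any marker is estimated.** Both points are true. The age group with 12 ferric maltol subjects is likewise an illustration. Confidence intervals are planned only where applicable.
- **The departure is stated openly in the SAP, and amending the protocol would also remove the conflict.** An SAP clause does not lift a protocol prohibition. An amendment would cure the conflict but would not supply a suitable value to carry to Week 4.

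**Conclusion.** The point holds. It is certain that LOCF contradicts protocol 12.2.4, is missing from section 5, and has no suitable scheduled value to carry to Week 4. The 2.5% to 10.9% share of ferric maltol Week 4 values is conditional on PK samples counting, on the assumed 5% to 20% missing, and on full recruitment of 49 per arm. The infant figures also depend on PK samples counting, and the Week 4 one on treating an unscheduled value as missing.

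For Week 12 at ages 2-17 the issue is narrower. Both arms have a scheduled Week 4 value, so what remains is the departure from the protocol and a value 56 days old shown as Week 12.

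The endpoint is secondary and descriptive. Type I error, power and the primary haemoglobin model are unaffected. This should be corrected but does not threaten the trial's main conclusion.

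**What to change.** In SAP 3.4.2:

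1. Delete the LOCF sentence and summarise observed Week 4 and Week 12 iron-marker values, as protocol 12.2.4 requires.
2. Add one sentence stating that post-dose PK-day samples are not used for change from baseline to Week 4 or Week 12.
3. State that no Week 4 iron-marker summary is produced for subjects under 2 years.

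The cost is SAP wording only, with slightly fewer subjects in the two summaries. Those left out would include subjects whose later values 3.4.2 already excludes after transfusion, intravenous iron or an ESA. Showing the number with data at each visit makes the loss visible.

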7.5 INDIVIDUAL DISCONTINUATION CRITERIA

Subjects and/or their parents or guardians have the right to withdraw consent without prejudice at any time during the study. If a subject withdraws consent, the Investigator should make a reasonable effort to determine the cause. All withdrawn subjects should have a Post-Treatment Safety Visit within 10-14 days after the last dose of study drug (if the subject agrees in the case of withdrawn consent).

If there is any sign of accumulation of maltol or glucuronide in the pre-assignment phase PK day for subject population aged 1 month to less than 2 years, the recruitment to this age group will be suspended and they will not enter the treatment phase until the risk has been assessed and approved via a substantial amendment to the protocol.

Subjects may be discontinued prematurely during the study for the following reasons:

- Withdrawal of informed consent
- A drop of >1 g/dl in Hb from baseline
- Unwillingness or inability to comply with protocol requirements
- Pregnancy or not using a reliable method of birth control (female subject of childbearing potential)
- Use of prohibited concomitant medications
- Serious adverse events that are judged by the Investigator to be related to study treatment

CONFIDENTIAL Page 47 of 80

- Blood transfusions for any cause during the study treatment period
- Use of any other single agent prescribed iron medications
- Occurrence of any condition that, in the opinion of the Investigator, significantly
 jeopardizes the wellbeing and safety of the patient, including any intolerable toxicity
 related to study treatment determined by the investigator to be unacceptable given
 the severity of the event

The reason for study drug discontinuation and the date of last dose should be recorded in the eCRF. Subjects who discontinue treatment prematurely must return for the Post-Treatment Safety Visit, unless informed consent is withdrawn (and the subject and/or their parents or guardians do not agree to attend this follow-up visit). A subject who meets discontinuation criteria should be discussed on an individual basis with the Medical Monitor.

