3.1.4 Summary Statistics

Categorical data will generally be summarised with counts and percentages of subjects. The denominator used for the percentage calculation will be clearly defined. Continuous data will

generally be summarised with descriptive statistics including n (number of non-missing values), mean, median, standard deviation, range (minimum and maximum).

For PK parameters, descriptive statistics will also include coefficient of variation (CV %), geometric mean (GM) and GM CV (%).

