3.1.6 Handling of Dropouts and Missing Data

In general, missing data will not be imputed unless otherwise specified. Only observed data will be used in the summaries and analyses.

For adverse events (AEs) with incomplete or missing dates, imputation for start and stop dates relative to the start date of study drug is necessary to define an AE as treatment emergent. For missing AE start day, the 1st of the month will be used. If this day is before the day of study drug start and the end date of AE is on or after the date of first study drug, or if the AE end date is completely missing, the start date of study drug will be used. For missing start day and month, the start day and month will be January 1st. If January 1st is before start day and month of study drug, the start date of study drug will be used.

Partial dates for concomitant medications will be imputed to determine prior and concomitant status. Partial dates will be imputed as above for AEs. If the start date is completely missing, the start date will equal the date of first study drug. If the stop date is known and prior to the first date of study drug, the start date will equal the stop date of concomitant medication. If the stop date is completely missing, the concomitant medication will be considered as ongoing.

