3.4 Efficacy Assessment

Efficacy data will be summarised by randomised/assigned treatment based on the mITT Population for the primary and on the ITT Population for the secondary endpoints. Sensitivity analysis will be performed on the ITT Population for the primary endpoint.

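### The SAP sets no denominator and no non-responder rule for the Week 12 normal-Hb rate, and its observed-data rule conflicts with the ITT Population it names

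*SAP*

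**What the plan says.** SAP 3.4.2 specifies this summary in one sentence: "The number and percentage of subjects achieving normal range" at Week 12, judged against the central laboratory's range, is reported by arm. The sentence gives no denominator and no rule for a child without a Week 12 Hb. SAP 3.1.4 promises in general that the "denominator used for the percentage calculation will be clearly defined", but no definition follows for this endpoint.

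Three other rules bear on it:

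- **Missing data.** SAP 3.1.6: "Only observed data will be used in the summaries and analyses". Protocol 12.2.4 agrees: "All data will be used according to availability, with no imputation for missing data". SAP 3.4.2 makes one exception, last observation carried forward, and only for the iron markers. Hb is not among them.
- **Values after rescue.** SAP 3.4.2 removes some values from the secondary analyses: "Any measurement obtained after a patient received a blood transfusion" is excluded, as is any taken after intravenous iron or an ESA. Nothing says that the child then counts as not achieving.
- **Population.** SAP 3.4 summarises efficacy "on the ITT Population for the secondary endpoints". SAP 3.2.1 defines that population as everyone randomised or assigned.

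**The concern.** The observed-data rule points to a percentage among children who have a Week 12 Hb. The ITT statement points to a percentage among all children in the arm. Two programmers could follow the SAP faithfully and report different rates.

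The difference is unlikely to be neutral, because the reasons for a missing value overlap with treatment failure. Protocol 7.5 lists among the grounds for stopping "A drop of >1 g/dl in Hb from baseline", a transfusion, other prescribed iron and intolerable toxicity. A child who stops is sent to the post-treatment safety visit (Visit 7), and the protocol schedules no Day 84 visit for that child. If such children are left out, the endpoint becomes normal Hb among those who stayed on treatment long enough to be measured.

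The first primary objective is to compare tolerability between the products, so unequal stopping is a real possibility. An arm that loses more of its failures would then look better on this endpoint than it should.

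**Working it through.** **The plan's own figure.** The documents give no expected rate, sample size or power for this endpoint. Their only power figure, at least 80% with 49 ferric maltol subjects, concerns mean Hb change (true change 0.5 g/dL, SD 1.2 g/dL). It reproduces: 0.5/(1.2/√49) = 2.917; 2.917 − 1.960 = 0.957; Φ(0.957) = 83.1%. The noncentral t gives 81.5%. It has no bearing on the responder rate.

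**Who lacks a Week 12 Hb.** Visit 7 falls 10 to 14 days after the last dose (protocol 7.5). SAP 3.6.2 says haematology is collected there for early discontinuers. Protocol 10.3 and 10.4 list no haematology at Visit 7 and make it a telephone visit by default. SAP 3.1.2 maps early-termination values from Day 71 onward to Day 84. If the sample is taken and mapped that way:

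- Last dose before Day 57: Visit 7 is at latest Day 56 + 14 = Day 70, so there is no Week 12 value.
- Last dose on Day 57 to 60: it depends on the date of Visit 7 (57 + 14 = 71, but 60 + 10 = 70).
- Last dose on Day 61 or later: Visit 7 is at earliest Day 61 + 10 = Day 71, so there is a Week 12 value, taken off treatment.

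If Visit 7 stays a telephone call, as in the protocol, later stoppers can be lost as well.

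**Size.** Let N be the ITT count in the arm, c the number with a usable Week 12 Hb, and x the number in normal range.

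- Observed-case rate = x/c
- ITT rate, missing counted as not achieving = x/N
- Ratio of the two = N/c

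Inputs: N = 49 (protocol 12.1, SAP 2.2.4). For c/N, the adult IBD study in protocol 5.4.1 had 87% completing 12 weeks on ferric maltol and 82% on placebo; 95%, 75% and 70% are assumed. For x/c, that study reports 65% normal at Week 12. Protocol 5.4.1 does not say whether those 65% are of all randomised or of completers, so applying it to children with a value is also an assumption. Counts are rounded to whole children.

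| c/N | c | x | x/c | x/N | Gap (points) |
|---|---|---|---|---|---|
| 95% | 47 | 31 | 66.0% | 63.3% | 2.7 |
| 87% | 43 | 28 | 65.1% | 57.1% | 8.0 |
| 82% | 40 | 26 | 65.0% | 53.1% | 11.9 |
| 70% | 34 | 22 | 64.7% | 44.9% | 19.8 |

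At 87%, N/c = 49/43 = 1.14, and 57.1% × 1.14 = 65.1%.

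**Unequal stopping.** Take 43 of 49 assessed in one arm and 37 of 49 in the other (75%, assumed). The observed-case rates are 28/43 = 65.1% and 24/37 = 64.9%, almost the same. The ITT rates are 28/49 = 57.1% and 24/49 = 49.0%, a difference of 8.1 points that the observed-case summary would hide.

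**The case against.** A reader might infer that the plan removes failures from the denominator and that the reported rate will be overstated. The documents do not go that far. SAP 3.4 names the ITT Population, and a ban on imputation forbids inventing Hb values without saying that children lacking one leave the count. On an ITT denominator they already count as not achieving, and the overstatement is zero. The transfusion rule removes a measurement, not a child, and with an ITT denominator it prevents a false responder. This stands as a second open reading. It does not settle the matter, because naming a population does not classify a member who has no value, and the missing-data rules offer no classification either.

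A reader might also infer that every child who stops has no Week 12 Hb. That is too broad: SAP 3.6.2 and the visit windows can recover many later stoppers.

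Nor are all missing values failures. An Hb drop is a ground on which a child may be stopped, discussed with the Medical Monitor. In the 2 to 17 age group, scheduled post-baseline Hb is only at Days 28 and 84, so before Week 12 scheduled testing can reveal such a drop only at Day 28. Intolerance and poor compliance say nothing direct about Hb.

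Finally, SAP 3.3.1 tabulates discontinuations and their reasons by treatment. With the number achieving also shown, a reader could rebuild the all-randomised rate. That limits the harm but leaves the headline percentage undefined.

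**Conclusion.** The point holds as an undefined denominator together with a conflict between two stated rules. The observed-case reading follows most directly from the observed-data rule, from the carry-forward exception limited to iron markers, and from the exclusion of values after transfusion, intravenous iron or ESA. If it is used, the rate is inflated by N/c relative to an ITT rate: about 8 points at 13% missing and 65% observed, and about 3 to 20 points for 5% to 30% missing. These sizes rest on adult or assumed figures. If the ITT count is used, there is no inflation, so actual overstatement cannot be claimed from the documents. The children affected are mainly those who stop before about Day 57 to 61, or later if the Visit 7 sample is not taken.

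SAP 3.1.5 makes the endpoint secondary and descriptive, so no type I error is affected. It is still the trial's responder measure, reported by arm, and the ambiguity should be removed.

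**What to change.** Add to SAP 3.4.2 text to this effect: *The denominator is all ITT subjects in the arm and age group. A subject with no Week 12 Hb, or whose Week 12 Hb follows a transfusion, intravenous iron or an ESA, is counted as not achieving normal range.*

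Keep the observed-case percentage as a supportive row, with the number missing by reason and arm, and list the change in SAP section 5. The protocol schedules and SAP 3.6.2 should also be reconciled on whether haematology is taken at Visit 7 after early discontinuation, since that decides who has a value.

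The cost is one paragraph and a few table rows. The downside is a somewhat less favourable rate, because children missing for administrative reasons also count as not achieving. The supportive row and the reasons for missing values let a reader judge how much that matters.
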